8.1.3 Serious adverse events

A Serious Adverse Event (SAE) refers to an untoward medical occurrence such as death, life-threatening event, permanent or serious disability or loss of function, need for hospitalization or prolongation of hospitalization, and congenital abnormalities or birth defects, after the subject receives the investigational drug; other major medical events: Medical and scientific judgment should be exercised in deciding whether expedited reporting is appropriate in other situations, such as major medical events that may not be immediately life-threatening or result in death or hospitalization or may require medical intervention to prevent one of the other outcomes listed in the above definition. such as major treatment in the emergency room or allergic bronchospasm at home, cachexia or convulsions of subjects not hospitalized, drug dependence or addiction, etc.

8.1.4 Suspected unexpected serious adverse reaction

A Suspected Unexpected Serious Adverse Reaction (SUSAR) refers to a suspected unexpected serious adverse reaction whose nature and severity of clinical manifestations exceed those in the Investigator's Brochure of the investigational drug, the package inserts of the marketed drug or the summary of product characteristics.

Expectedness determination: it should be evaluated according to the related chapters in the Investigator's Brochure (the effective version on the date of the event occurrence) as safety reference information. Unexpectedness refers to an event that is not listed in the Investigator's Brochure or is not listed with the specificity or severity that has been observed for the

investigational drug.

The investigator is responsible for evaluating the relationship between all AEs and the investigational drug. The principal investigator can entrust other qualified clinicians participating in this study to make judgments, but he/she still needs to be responsible for this. The investigator must provide a list of persons who have the corresponding qualifications and accept the commission.

Protocol No.: HTD1801.PCT103

8.2 Causality

The causal relationship between the investigational drug and events can be classified into definitely related, possibly related, doubtfully related, not related, and undecidable.

Definitely related	The AE follows a reasonable temporal sequence from administration of the study intervention, follows a known or expected response pattern to the investigational drug, that is confirmed by improvement on stopping and reappearance of the event on repeated exposure (i.e., the re-challenge test is positive) and other confounding factors such as the fact that original diseases have been ruled out.
Possibly related	The reaction follows a reasonable temporal sequence from administration of the study intervention and follows a known or expected response pattern to the investigational drug, but that could readily have been produced by the subject's clinical state or other treatment methods.
Doubtfully related	The reaction doesn't follow a reasonable temporal sequence from administration of the study intervention, and doesn't follow a known or expected response pattern to the investigational drug, that could readily have been produced by the subject's clinical state or other treatment methods.
Not related	The reaction doesn't follow a reasonable temporal sequence from administration of the study intervention, and follows a known or expected response pattern to non-investigational drug. That could readily have been produced by the subject's clinical state or other treatment methods. The response is resolved when disease is relieved or other treatment methods are stopped. The reaction appears when other treatment methods are reused, and is closely related to other risk factors.
Undecidable	There is no clear temporal sequence relationship between the time of the reaction and the time of drug administration. The reaction follows a similar pattern to the known response pattern of the investigational drug. Same reaction could be produced by other drugs. There is no sufficient basis for judgment.

When the SAE report in this study was further evaluated for compliance with the accelerated reporting criteria for Suspected Unexpected Serious Adverse Reactions (SUSARs), if its causality assessment was "doubtfully related", it was classified as "not related" in the dichotomy.

8.3 Criteria for Determining the Severity of AEs

The severity of AEs should be judged according to the CTCAE 5.0. If there are AEs not listed in the table, the following criteria can be referred to:

Grade 1: Mild; asymptomatic or mild symptoms; clinical or diagnostic observations only; intervention not indicated;

Grade 2: Moderate; minimal, local or noninvasive intervention indicated; limited age-appropriate instrumental activities of daily living (ADL) (instrumental ADL refer to preparing meals, shopping for groceries or clothes, using the telephone, managing money, etc.);

Grade 3: Severe or medically significant but not immediately life-threatening; hospitalization or prolongation of hospitalization indicated; disabling; limited self care ADL (self care ADL refer to bathing, dressing and undressing, feeding self, using the toilet, taking medications, and not

bedridden);

Grade 4: Life-threatening consequences; urgent intervention indicated;

Grade 5: Death related to AE.

Note: The CTCAE terms provide the grading of specific laboratory abnormalities. Grade 4 laboratory abnormality does not automatically indicate a life-threatening event. Abnormal laboratory results still need to be evaluated for AEs.

Protocol No.: HTD1801.PCT103

8.4 Measures Related to Investigational Drug

- Discontinuation The investigational drug is discontinued due to a specific AE.
- Dose unchanged No discontinuation of the investigational drug is required for a specific AE.
- Unknown Only used when the measures to be taken cannot be determined.
- Not applicable The investigational drug is discontinued for reasons other than a specific AE, e.g.: study was terminated, subject died, the investigational drug was discontinued prior to the occurrence of an AE.
- Dose interruption The investigational drug is temporarily interrupted (suspended) (including voluntary interruption by the subject) due to a specific AE and following resumption of the drug.

8.5 The Outcome of Adverse Events Can Be Described as The Following:

- Recovered/resolved: "Termination date of (serious) adverse event" should be indicated.
- Recovering/Resolving: The event has not yet been completely resolved, but the subject is already in the recovery phase. Follow-up is needed.
- Unrecovered/Unresolved: The event is in progress.
- Recovered/resolved with sequelae: only if the subject has long-term or lifelong sequelae, such as blindness caused by diabetes and hemiplegia after stroke. "Termination date of (serious) adverse event" should be indicated.
- Fatal: "Termination date of (serious) adverse event" should be indicated. For death caused by AEs, the time of death shall be recorded.
- Unknown: The investigator cannot be informed of the AE, for example, the subject is lost to follow-up.

If the outcome of the AE is assessed as "recovering/resolving", or "unrecovered/unresolved", or "unknown", it is temporarily not necessary to record the termination date of the AE.

If the outcome of the AE is assessed as "recovered/resolved" or "recovered/resolved with sequelae", the termination date of the AE must be recorded.

8.6 Collection, Recording and Reporting of AE

8.6.1 Collection and reporting of AE

AE collection phase

The AEs should be collected since the subject signs the ICFs to participate in the study until the end of 4-week (28-day) safety follow-up visit after the subjects' last dose of the investigational drug. Regardless of its severity, or relationship to the investigational drug, all AEs should be

documented on the appropriate pages of the original medical record and the eCRF.

Adverse medical events that occurred during the screening phase are recorded as the medical history. Adverse medical events in the single-blind introduction period, double-blind treatment phase and safety follow-up visit phase are recorded as AEs; if the severity meets the SAE severity criteria, the adverse medical events are recorded as SAEs.

Protocol No.: HTD1801.PCT103

In order to ensure the safety of the subjects, the investigator should take appropriate measures to track all AEs until the AEs are recovered and stabilized, have other explanations, or the subject is lost to follow-up. This means that observation may still be required after the last visit as specified by the protocol.

Reporting of AEs

At each study visit, the investigator will assess the occurrence of subjective AEs. The investigator can ask a neutral question such as "How have you been feeling since your last visit?". Subjects can report AEs that occur at any other time during the study. All AEs, related or not related to the investigational drug, should be followed up until normal status or remission, or restoration to baseline levels, or the investigator determines that there is no need to continue follow-up, or the subject is lost to follow-up. All AEs will be recorded on the AEs page of the eCRF, regardless of whether the investigator concludes that the event is related to drug treatment.

When reporting an AE, a single diagnosis or syndrome rather than a symptom should be used to describe the AE as far as possible. Investigators should record the onset and end dates of AE symptoms, the severity of AEs and their severity criteria (applicable to SAEs and meet the judgment criteria for SAEs), assessments of the correlation of AEs to the investigational drug or study procedures, measures taken for the investigational drug, the treatment given for AEs and the outcome of AE, etc. in detail.

Subject diaries will not be used as the primary means of collecting AEs. However, if the investigator identifies a potential AE from the information gathered from these documents, the subject should be followed up appropriately for medical evaluation. With this follow-up visit, if a previously unreported AE is identified, such AE should be reported according to the normal reporting requirements.

8.6.2 Collection and reporting of SAEs

For all SAEs that occur within the collection time limit specified in the study protocol, the investigator must fill in the "SAE Report Form" within 24 hours of notification, sign, date, and send it to the Sponsor and Sponsor representative (CRO assigned by the Sponsor) immediately by fax or email (as follows), and appropriate treatment measures should be administered immediately to the subject.

Sponsor email: [contact]

CRO Email: [contact]

The investigator should provide detailed and written follow-up reports in a timely manner. For SAE follow-up information, the reporting method is the same as the initial report.

For the reporting of death events, the investigator should provide the Sponsor and the Ethics Committee with required data, such as autopsy report and final medical report.

8.7 Reporting of SUSARs

After the Sponsor and/or Sponsor representative receive safety-related information from any source, they should immediately conduct a comprehensive analysis, evaluation and judgment,

including severity, correlation with the investigational drug, and whether it is an expected event. A expedited report should be made according to the time limit set by the regulatory authority based on the nature (category) of the event. The Sponsor and/or Sponsor representative should submit expedited report of SUSAR to all investigators and study sites participating in the clinical study, the ethics committees, drug regulatory authorities, and health authorities within the prescribed time limit. For specific expedited reporting standards and procedures, please refer to the *Standards and Procedures for the Expedited Reports of Safety Data during Clinical Trials* and *Frequently Asked Questions on Expedited Reporting of Safety Data during Clinical Trials (Version 1.0)* issued by Center for Drug Evaluation (CDE), National Medical Products Administration.

Protocol No.: HTD1801.PCT103

There is no time limit for collection of SAEs judged to be related (definitely related, possibly related, doubtfully related, undecidable) to the investigational drug. This means that investigational drug-related SAEs that occur after the last visit specified in the protocol still need to be reported. The reporting method for SUSAR that occurs after the end of the clinical study and before the approval conclusion is the same as the expedited reporting method before the end of the study.

For the SUSAR report and study-related safety information provided by the Sponsor, the investigator should read them in time, and report them to the study sites and ethics committee.

8.8 Definition of Hospitalization

AEs requiring hospitalization are considered as SAEs. Generally speaking, hospitalization is for admission procedures and treatment, and this AE should be considered as an SAE.

Hospitalizations due to elective surgery, routine clinical procedures, annual check-ups, hospitalization observation or protocol requirements (not due to AEs) are not considered as AEs, but needs to be filled in the clinical evaluation form and included in the eCRF. If an unexpected event occurs during this process, it should be reported as a "serious" or "non-serious" AE according to conventional standards.

Note: Hospitalization or extension of the hospitalization period due to non-medical reasons/convenience reason, etc. or only for clinical study purposes does not meet the criteria for medical events and therefore cannot be regarded as a SAE.

8.9 Pregnancy

If any female subject or partner of a male subject becomes pregnant or is found to be pregnant during the study (from signing the ICFs to within 4 weeks [28 days] after the last dose of the investigational drug), the investigator must record this information in the Pregnancy Event Form and submit it to the Sponsor. The investigator should follow up the pregnancy results until obtaining the pregnancy outcome (e.g., termination of pregnancy, delivery).

If pregnancy outcome meets the criteria for an SAE (e.g., spontaneous abortion, stillbirth, neonatal death, or congenital malformation), the investigator should report it according to the procedure for reporting SAEs.

Other pregnancy outcomes considered as SAEs: "spontaneous abortion", including inevitable and missed abortion.

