also be passed through breast milk, which raises some concerns about using BBR while breastfeeding.

Protocol No.: HTD1801.PCT103

For "exacerbation of jaundice and kernicterus in neonates with G6PD deficiency", the clinical indication of HTD1801 is for adult subjects only, so this safety risk dose not exist. In addition, the inclusion/exclusion criteria for the clinical study clearly stipulated those subjects who have any disease that may cause hemolysis or unstable red blood cell count and affect the HbA1c test, such as hemolytic anemia, etc., should not be included in this study.

Based on the results of previous studies, in the clinical studies of HTD1801 completed in the United States, Australia and Canada, the maximum dosing duration are 18 weeks, and female subjects of childbearing potential were included. No drug-related SAEs were observed in these studies. Although developmental toxicity that may cause concern has not been detected in the reproductive toxicity studies that have been completed so far, in order to further ensure the medication safety of subjects, it is necessary to definitely control reproductive risks in the clinical study protocol, including but not limited to the following:

- a) Pregnant or lactating female subjects should be excluded; female subjects of childbearing potential are eligible for inclusion in this study only if they are negative in the pregnancy test at screening (V1) and before randomization (V3);
- b) Subjects should be strictly screened and take contraceptive according to the study protocol; if the partners of the male subjects or the female subjects are planning to become pregnant, or are unwilling to take reliable contraceptive measures (see APPENDIX 6) during the period from the signing of the informed consent forms (ICFs) to 3 months after the last dose of the investigational drug, the subjects should be excluded;
- c) Pregnancies in female subjects of childbearing potential should be followed up throughout the study.

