 - eGFR < 60 mL/min/1.73 m² (see APPENDIX 5 for calculation formula); or urine protein \geq ++.
- 31. Subjects who have donated blood or had massive blood loss (≥ 400 mL), or received

blood transfusion or blood products within 3 months prior to screening.

32. Subjects who are alcoholism (14 units of alcohol per week: 1 unit = 285 mL beer, or 25 mL liquor, or 100 mL wine) within the 12 months prior to screening and are unable to control alcoholism during the study.

Protocol No.: HTD1801.PCT103

- 33. Pregnant or lactating female subjects.
- 34. Partners of the male subjects or the female subjects are planning to become pregnant, or are unwilling to take reliable contraceptive measures (see APPENDIX 6) during the period from the signing of the ICFs to 3 months after the last dose of the investigational drug.
- 35. Subjects who have participated in clinical studies on other investigational drugs or medical devices, and taken investigational drugs or used medical devices, or used any unapproved treatment methods within 3 months prior to screening.
- 36. Subjects who have received vaccines (except inactivated vaccines) within 4 weeks prior to screening or planned to receive the vaccines (except inactivated vaccines) during the study (from the signing of the ICFs to the end of the safety follow-up visit).
- 37. Subjects who have the medication compliance <80% or >120% in the single-blind introduction period.
- 38. Subjects who are considered as not suitable for participating in the study by the investigator due to other conditions.

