4.3.8 V8: Safety follow-up visit (Week 16 (Day 112) \pm 3 days)

V8 is a telephone follow-up visit to inquire about the occurrence of AEs, and collecting information on concomitant medication and non-drug treatment; if the subject has abnormal results in previous laboratory tests or other tests, the investigator may arrange the subject to receive the test or examination again in the hospital based on the clinical judgment.

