APPENDIX 5: Calculation Formula

Calculation Formula for Glomerular Filtration Rate (GFR)

GFR is calculated using the CKD-EPI formula:

Serum creatinine unit conversion: 1 mg/dL = $88.4 \mu mol/L$

Gender	Scr Range	EPI-GFR Formula, unit: mL·min ⁻¹ · (1.73 m ²) ⁻¹
		EPI-GFR= $144 \times [Scr(mg/dL) / 0.7)]^{-0.329} \times 0.993^{age}$
	Scr > 0.7mg/dL	EPI-GFR= $144 \times [Scr(mg/dL) / 0.7)]^{-1.209} \times 0.993^{age}$
Male	$Scr \leq 0.9 mg/dL$	EPI-GFR= $141 \times [Scr(mg/dL) / 0.9)]^{-0.411} \times 0.993^{age}$
	Scr > 0.9mg/dL	EPI-GFR=141×[Scr(mg/dL) / 0.9)] ^{-1.209} ×0.993 ^{age}

Protocol No.: HTD1801.PCT103

QTcF Calculation Formula

QTcF=QT/RR^{0.33} (RR is the normalized heart rate)

APPENDIX 6: Birth Control, Definition of Female Subjects of Childbearing Age, and Contraception Requirements

Protocol No.: HTD1801.PCT103

> Definition of Female Subjects of Childbearing Age

Female subjects of non-childbearing age are defined as postmenopausal female subjects and premenopausal female subjects who had undergone sterilization. Postmenopause is defined as the absence of menstrual periods for ≥12 consecutive months without alternative medical measures. FSH >40 MlU/mL can be determined as menopause by follicle-stimulating hormone (FSH) test in uncertain subjects. Sterilization procedures include bilateral tubal ligation or bilateral oophorectomy or hysterectomy.

Female subjects of childbearing age are defined as women who are anatomically and physiologically able to get pregnant without sterilization from menarche to menopause.

> Contraception Requirements

Female subjects of childbearing age must be negative in the pregnancy test at the screening phase;

During the screening phase to the last dose, female subjects of childbearing age and male subjects must also agree to one of the following operations:

- Complete abstinence of sex activities. Periodic abstinence (e.g., calendar, ovulation, symptom-temperature, postovulation method) is not permitted.
- One of the contraceptive methods with <1% correct failure rate:
 - Intrauterine device (IUD) or intrauterine hormone-releasing systems with an annual failure rate < 1%
 - Vasectomy for male subjects;
 - Double-barrier method of contraception: condom and/or occlusive cap (diaphragm or cervical cap/dome cap), a barrier method with spermicide (foam/gel/film/cream/suppository) must be used as a supplementary measure.

The following contraception methods can be accepted within 3 months after the last dose:

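### Pregnancy notification stops 28 days after the last dose, although the protocol's own pregnancy-avoidance period runs to 3 months

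*Protocol*

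**What the plan says.** Section 8.9 sets the reporting rule. For a pregnancy in a female subject or in the partner of a male subject, "the investigator must record this information in the Pregnancy Event Form and submit it to the Sponsor". The period is "from signing the ICFs to within 4 weeks [28 days] after the last dose of the investigational drug". For pregnancies inside it, "The investigator should follow up the pregnancy results until obtaining the pregnancy outcome". Certain outcomes, including spontaneous abortion, stillbirth, neonatal death and congenital malformation, are handled as SAEs.

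Three other places set a longer period for avoiding pregnancy:

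- Section 3.2, exclusion criterion 34, excludes anyone planning a pregnancy or unwilling to use reliable contraception "during the period from the signing of the ICFs to 3 months after the last dose of the investigational drug".
- Section 1.4, item b), repeats this as a control on reproductive risk: "during the period from the signing of the informed consent forms (ICFs) to 3 months after the last dose of the investigational drug".
- Appendix 6 introduces a list of methods with "The following contraception methods can be accepted within 3 months after the last dose".

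One clause reaches beyond 28 days. Section 8.7 states: "There is no time limit for collection of SAEs judged to be related (definitely related, possibly related, doubtfully related, undecidable) to the investigational drug".

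**The concern.** The protocol treats the 3 months after dosing as a period in which pregnancy must be avoided, but it requires failures of avoidance to be recorded only for the first 28 days. Section 1.4 lists fetal harm as one of two potential safety issues of the berberine moiety and says that reproductive risk must be controlled through the protocol.

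What is at stake is interpretation. If a late miscarriage or malformation reaches the sponsor as an SAE, there is no count of late pregnancies and no record of normal outcomes to set it against. In a trial of 99 subjects such events will probably be few, so each one would have to be read individually, and the missing context matters more for that reason.

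**Working it through.** The protocol states no figure on this point, so there is nothing to reproduce. The check compares the two periods and then asks whether any other clause closes the gap.

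**The two periods**

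| Rule | Source | End, counted from last dose |
|---|---|---|
| Pregnancy Event Form | 8.9 | 28 days |
| General adverse event collection | 8.6.1 | 28 days |
| Willingness to avoid pregnancy | 3.2 (criterion 34), 1.4 b) | 3 months |
| Accepted contraceptive methods | Appendix 6 | 3 months |

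**Size of the gap.** The protocol does not define 3 months in days, so I assume 84 (twelve weeks), 90 or 92 days.

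Uncovered share = (avoidance days − 28) / avoidance days

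- 84 days: (84 − 28)/84 = 56/84 = 0.667
- 90 days: (90 − 28)/90 = 62/90 = 0.689
- 92 days: (92 − 28)/92 = 64/92 = 0.696

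Subjects assigned to HTD1801: 33 + 33 = 66 of 99. The other 33 receive placebo. The 66 is an upper bound on exposed subjects, not the number who could have a pregnancy to report.

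**Could another clause capture a pregnancy beginning after day 28?**

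1. *The wording of 8.9.* It covers a pregnancy that begins, or is discovered, within the period. One conceived by day 28 and discovered later is arguably covered. One conceived after day 28 is not.
2. *Section 8.7.* It removes the time limit only for SAEs, and only for those not judged unrelated. Under 8.9 a pregnancy is not itself an SAE; only certain outcomes are. A normal delivery, or an SAE judged not related, is not captured.
3. *Section 8.6.1.* Routine adverse event collection ends at the same 28 days.
4. *Section 1.4, item c).* It asks for pregnancies to be followed over the course of the study. It adds no time beyond the study and refers only to female subjects, not to partners.
5. *Section 4.3.8.* "V8 is a telephone follow-up visit to inquire about the occurrence of AEs" and about concomitant treatment. No pregnancy question is listed. The last scheduled pregnancy test is at V7 (section 7.3.5).

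None of these requires notification of a pregnancy beginning on about days 29 to 90.

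**The case against.** The strongest reply is that the two periods govern different things, so nothing is contradicted. The 3 months is an eligibility condition on intention and contraception. Section 8.9 is a reporting rule, and its 28 days match adverse event collection, the V8 call and the end of the study. No passage promises notification to 3 months. This stands as far as it goes: the point is a design choice, not a broken commitment. It does not explain why a period judged to need avoidance is not also one in which failures are recorded, and the protocol gives no reason.

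A second reply is that the document shows no risk from conceptions this late. Section 1.4 says the completed reproductive studies raised no developmental toxicity of concern, and section 1.2.3.2 reports rapid elimination in rats without significant accumulation. That is fair, and no risk from late conception is demonstrated here. But those data would support a shorter avoidance period. They do not support keeping 3 months of avoidance with 28 days of notification.

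Third, the outcomes of most concern are already collected under 8.7, whose definition of related is broad and includes doubtful and undecidable cases. This is correct and limits the gap considerably. What remains is the count of late pregnancies, their normal outcomes, and SAEs judged not related.

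Finally, the affected group is small. Ages run to 75, some women are postmenopausal or sterilised, and men count only through partners. The documents do not allow an expected number of pregnancies to be calculated. That also stands, and it is why the point is rated minor.

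**Conclusion.** The concern holds as a minor inconsistency in safety reporting. The notification rule ends at day 28, the avoidance rule ends at 3 months, and no other clause requires notification of a pregnancy beginning in between. The uncovered interval is 56 to 64 days, or 67% to 70% of the post-dose avoidance period, if 3 months means 84 to 92 days. This measures calendar time only and says nothing about how many pregnancies would be missed or how risky they would be. The mismatch in dates is certain from the text. The practical consequence is probably small, and there is no effect on the efficacy analysis or on power.

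**What to change.** In section 8.9, replace the 28-day limit with 3 months after the last dose. Because the present limit sits in a parenthesis that defines the study period, it is cleaner to state the notification period in its own right, for example: *from signing of consent until 3 months after the last dose, whether or not the study has ended*. At the V8 call (section 4.3.8), add an instruction that subjects report any pregnancy, their own or a partner's, up to that date.

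The cost is one phrase and one instruction at a contact already planned, with no added visit. The downside is reliance on self-report for about two months after the last scheduled contact, plus some pregnancy follow-up after it. If the sponsor wants active capture, one further telephone call at 3 months would provide it.
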